APPENDIX 3: INVESTIGATOR-RATED ASSESSMENT OF SIGNS OF MEIBOMIAN GLAND DYSFUNCTION

The investigator will rate the bilateral severity of the subject's MGD signs according to the following classification and for each eyelid:

1. Total MGD Score

A digital expression by applying pressure with thumb or forefinger will be used to express the meibomian gland of the UPPER eyelids. A cotton tip applicator is preferred but not required to evaluate the LOWER eyelids meibomian glands.

The character of the secretion of 5 central glands on both the upper and lower eyelids will be evaluated for each eye. Each of the glands will be scored from 0-3:

0 = clear/slightly yellow

1 = opaque/yellow, whitish, particulate

2 = paste

3 = none/occluded.

The total score will thus range from 0-15 for each eyelid.

2. Eyelid Margin Vascularity

0 = Normal – Typical vascularity for subject age

1 = Mild vascular engorgement – Slightly dilated and pink blood vessels

2 = Moderate vascular engorgement – Slightly more dilated pink/red blood vessels

[figure not shown]
3 = Severe vascular engorgement – Multiple significantly dilated red blood vessels

4 = Very Severe vascular engorgement – Multiple significantly dilated deep red blood vessels

3. Bulbar Conjunctival Hyperemia

Investigator-Rated Assessment of Bulbar conjunctival hyperemia

Investigators will rate overall bulbar conjunctival hyperemia using the Cornea and Contact Lens Research Unit (CCLRU) Grading Scale.

- 0 = None
- 1 = Very Slight
- 2 = Slight
- 3 = Moderate
- 4 = Severe

APPENDIX 4: ETDRS BEST CORRECTED VISUAL ACUITY

Visual acuity testing should precede any examination requiring contact with the eye or instillation of study dyes, as is detailed in the order of assessments for each Visit in Section 5.1. Logarithm of the Minimal Angle of Resolution (LogMAR) visual acuity must be assessed using an ETDRS or modified ETDRS chart. Visual acuity testing should be performed with best correction using subject's own corrective lenses (spectacles only) or pinhole refraction.

An ETDRS or modified ETDRS chart may be used. If a Lighthouse chart is used (24.5" by 25"; either reflectance or retro-illuminated), the subject must view the chart from a distance of exactly 4 meters (13.1 feet). If smaller reproductions (18" by 18", e.g., Prevent Blindness) are used, the subject viewing distance should be exactly 10 feet. Reflectance wall charts should be frontally illuminated (60 watt bulb or a well-lit room).

The subject should be positioned according to the elevation of the chart (either seated or standing) so that the chart is at a comfortable viewing angle. The right eye should be tested first. The subject should attempt to read each letter, line-by-line, left to right, beginning with line 1 at the top of the chart. The subject should be told that the chart has letters only, no numbers. If the subject reads a number, he or she should be reminded that the chart contains no numbers, and the examiner should then request a letter instead of the number. The subject should be asked to read slowly, about 1 letter per second, to achieve the best identification of each letter. He/she is not to proceed to the next letter until he/she has given a definite response. If the subject changes a response before he has read aloud the next letter, then the change must be accepted.

Maximum effort should be made to identify each letter on the chart; the subject should be encouraged to guess. When it becomes evident that no further meaningful readings can be made, the examiner should stop the test. The number of letters missed or read incorrectly should be noted.

In order to provide standardized and well-controlled assessments of visual acuity during the study, the same lighting conditions must be used consistently throughout the study.

Calculations: $\text{LogMAR VA} = \text{Baseline value} + (n \times 0.02)$

where:

the baseline value is the LogMAR number of the last line read (at least 1 letter read correctly in this line), and “n” is the total number of letters missed up to and including the last line read, and “0.02” is the value for each letter.

APPENDIX 5: SLIT LAMP BIOMICROSCOPY

The biomicroscopy exam should be performed with the slit-lamp using a beam width and intensity that provide optimal evaluation of the anterior segment.

This procedure will be performed in the same manner for all subjects observed at the Investigator's site. The site will record all ABNORMAL findings in the source document and the investigator will evaluate the ABNORMAL findings as Non-Clinically Significant (NCS) or Clinically Significant (CS). CS and NCS ABNORMAL findings will be recorded in the source documentation. However, only ABNORMAL CS descriptions will be captured in the eCRF.

Lashes

0 = Normal

1 = Abnormal

Eyelid

Edema

0 = Normal, no swelling of the lid tissue

1 = Abnormal

Skin

0 = Normal, including but not limited to thinning, pigment changes, dermatitis

1 = Abnormal

Conjunctiva

Edema

0 = Normal, no swelling of the conjunctiva

1 = Abnormal

Palpebral Conjunctival Erythema

0 = Normal, no redness of the conjunctiva

1 = Abnormal

Cornea

Infiltrates

0 = Absent

1 = Present

Endothelial Changes

0 = Normal, None

1 = Abnormal, pigment, keratoprecipitates, guttata

Edema

0 = Normal, None, transparent and clear

1 = Abnormal

Anterior Chamber

Cells

0 = Normal, No cells seen

1 = Abnormal (+ to +++ cells)

Flare

0 = Normal, No Tyndall effect

1 = Abnormal, Tyndall beam in the anterior chamber

Lens Pathology

0 = Normal, no opacity in the lens

1 = Abnormal, existing opacity in the lens; aphakic or pseudophakic eyes or other abnormal findings

Sclera

0 = Normal

1 = Abnormal

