3.2. DESCRIPTION OF TRIAL DESIGN

Design and Investigational Plan:

This is a multi-center, double-masked, randomized, vehicle-controlled, two cohort study. Subjects will be randomized into either 0.2% AXR-270 Cream (approximately 42 subjects in Cohort 1), 2.0% AXR-270 Cream (approximately 42 subjects in Cohort 2) or Vehicle (approximately 42 subjects) administered in both eyes.

Cohort 1:

Approximately sixty-three (63) subjects with a diagnosis of symptomatic posterior blepharitis associated with MGD meeting all inclusion/exclusion criteria at the Screening visit (Visit 1) will be asked to discontinue their eyelid hygiene regimen and use only Sponsor supplied commercial sterile eyelid wipes between Visit 1 and Visit 2 daily (Equalization Period). Subjects will then be evaluated at Baseline/Randomization (Visit 2; Week 0/Day 1) to confirm they continue to meet all inclusion/exclusion and are eligible for randomization. Note: The use of sponsor-supplied sterile eyelid wipes is to be discontinued after randomization at Visit 2. All subjects within this Cohort will be assessed for safety and exploratory efficacy. Both Investigator and subjects will be masked as to the IP. Subjects will be shown an instructional video on applying the investigational product to help ensure consistency in application across subjects. Further, the site should reinforce to the subject how to self-administer the IP to the eyelids and avoid ocular instillation. Subjects will self-administer a pre-specified volume (approximately 50 milligrams per eyelid) of 0.2% AXR-270 Cream or its Vehicle across the epidermis corresponding to the external surface overlying the tarsal plate of the upper and lower eyelids of both eyes. Refer to more detailed instructions in the Subject Dosing Instructions document. Blood draws for safety labs for all subjects will be performed prior to IP dosing in the clinic at Visit 2/Day 1. Following the in-clinic dose administration, subjects will be supplied with sufficient IP (2 tubes) to apply once daily at home in the evening during the treatment period. Subjects will self-administer IP QD in the evenings beginning on Day 2.

[figure not shown]
On the following week (Visit 3; Week 1/Day 8), the Investigators will examine the subject and perform all safety and efficacy assessments (excluding safety labs and dilated Ophthalmoscopy).

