8.2. ADVERSE EVENT DEFINITIONS

Adverse Event (AE): Any untoward medical occurrence associated with the use of an IP in humans, whether or not considered drug related.

Adverse Reaction (AR): Any AE caused by a drug. Adverse reactions are a subset of all suspected adverse reactions where there is reason to conclude that the drug caused the event.

Suspected Adverse Reaction (SAR): Any AE for which there is a reasonable possibility that the drug caused the AE. For the purposes of IND safety reporting, “reasonable possibility” means there is evidence to suggest a causal relationship between the drug and the AE. A SAR implies a lesser degree of certainty about causality than adverse reaction, which means any AE caused by a drug.

Unexpected: An AE or SAR is considered “unexpected” if it is not listed in the Investigator’s Brochure or is not listed at the specificity or severity that has been observed; or, if an Investigator’s Brochure is not required or available, is not consistent with the risk information described in the general investigational plan or elsewhere in the current application.

Life-threatening: An AE or SAR is considered “life-threatening” if, in the view of either the Investigator or Sponsor, its occurrence places the subject at immediate risk of death. It does not include an AE or suspected adverse reaction that, had it occurred in a more severe form, might have caused death.

A **SERIOUS ADVERSE EVENT (SAE)** is any AE or suspected adverse reaction occurring at any dose that:

- Results in death.
- Is life-threatening.
- Results in a persistent or significant incapacity or substantial disruption of the ability to conduct normal life functions.
- Requires inpatient hospitalization.
- Prolongs inpatient hospitalization.
- Is a congenital anomaly/birth defect.
- Is a significant medical event (i.e., one that may jeopardize the subject or may require intervention to prevent one or more of the other outcomes listed above).

A **NON-SERIOUS ADVERSE EVENT** is any AE that does not meet the definitions for SAEs as described above.

Each **AE** will be classified as **SERIOUS** or **NON-SERIOUS** using the definitions provided above.

The **SEVERITY** of each AE will be classified as **MILD**, **MODERATE**, or **SEVERE**. The Investigator will review each event and assess its **RELATIONSHIP** to use of IP (unrelated, unlikely, possibly, probably, definitely). The AE will be assessed using the following definitions:

Unrelated:

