8.3. PROCEDURES FOR AE REPORTING BY THE INVESTIGATOR

AEs will be monitored throughout the study and will be recorded on the eCRF with the date and time of onset, date and time of resolution, severity, seriousness, causality (relationship to use of IP), treatment required, and the outcome.

To elicit AEs, simple questions with minimal suggestions or implications should be used as the initial questions at all evaluation points during the trial. For example:

- How have you felt since your last assessment?
- Have you had any health problems since your last assessment?

The severity of each AE should be categorized as mild, moderate, or severe.

The causality of use of IP in relation to the AE will be assessed by the Principal Investigator after careful medical consideration and categorized as unrelated, unlikely, possible, probable, or definite.

If an AE occurs, the Investigator will institute support and/or treat as deemed appropriate. If a non-SAE is unresolved at the time of the last day of the study, an effort will be made to follow up until the AE is resolved or stabilized, the subject is lost to follow-up, or there is some other resolution of the event. The Investigator should make every attempt to follow SAEs to resolution.

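### The slit-lamp key files eyelid skin thinning, pigment change and dermatitis under grade 0 (Normal), at the site where the cream is applied

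*Protocol*

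**What the plan says.** The cream is applied to eyelid skin: Protocol section 3.2 has subjects spread it "across the epidermis corresponding to the external surface overlying the tarsal plate" of both lids in both eyes. Section 2.1 makes safety and tolerability the primary objective, and section 3.1.1 lists the slit-lamp and external eye exam as a safety endpoint.

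Appendix 5 gives the grading key for that exam. For eyelid skin, grade 0 reads "0 = Normal, including but not limited to thinning, pigment changes, dermatitis"; grade 1 is Abnormal with no description. The neighbouring items are built differently. Lid edema has "0 = Normal, no swelling of the lid tissue" and palpebral conjunctival erythema has "0 = Normal, no redness of the conjunctiva".

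The recording rule in the same appendix depends on the grade. "The site will record all ABNORMAL findings in the source document", and the investigator then judges each as clinically significant or not; "only ABNORMAL CS descriptions will be captured in the eCRF".

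SAP section 4.8.6 counts subjects with normal and abnormal results, eyelid skin among them, by treatment group and by study or non-study eye. The output is Table 14.4.2.5. Neither document defines the eyelid skin grade anywhere else.

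**The concern.** The key names three skin signs, so its authors evidently wanted them looked for, yet as worded it assigns them to Normal. The list is also open-ended, which leaves grade 1 with no defined content.

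A site that follows the text codes such a change 0. The change is then not an abnormal finding: no source note is required, no judgement of clinical significance is made, and the table counts the eye as normal. A literal reading can only remove skin changes from the abnormal count, so the error runs towards apparent safety. A site that reads through the slip codes the same change 1, so sites may differ.

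**Working it through.** No sample size or test is involved. The check compares the skin line with the rest of the key and then follows a grade through to the table.

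**1. The key, item by item (Appendix 5, 12 graded items)**

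| Form of the grade 0 line | Items | Count |
|---|---|---|
| Normal, with a statement of normality or absence | lid edema, conjunctival edema, palpebral erythema, endothelial changes, corneal edema, anterior chamber cells, flare, lens | 8 |
| Normal, with a list of signs | eyelid skin | 1 |
| Bare Normal | lashes, sclera | 2 |
| Absent/Present | corneal infiltrates | 1 |

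8 + 1 + 2 + 1 = 12. Of the 8 + 1 = 9 lines that describe grade 0 Normal, only the skin line lists signs. Where the key describes an abnormality elsewhere (endothelial changes, cells, flare, lens), it does so under grade 1. Either a negation was dropped or the list belongs one line lower. The line is complete and has its own grade 1 line beneath it, so a text-extraction fault is unlikely.

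**2. Route of a skin change to the outputs**

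| | Coded 1 | Coded 0 (literal reading) |
|---|---|---|
| Source note required | yes | no |
| Clinical significance judged | yes | no |
| Description in eCRF | only if clinically significant | no |
| Counted abnormal in Table 14.4.2.5 | yes | no |

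The lost eCRF description therefore concerns clinically significant changes only; the others would not be described there even if coded 1.

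**3. How often the line is used**

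Inputs: 126 subjects, of whom 42 + 42 = 84 are on active cream (section 3.2); three post-baseline exams, at Visits 3, 4 and 5 (Appendix 1).

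- All arms: 126 × 3 = 378 subject-visits, both eyes each time.
- Active arms: 84 × 3 = 252 subject-visits.

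**4. Size of the error**

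Let *s* be the share of eyes with such a change that are graded under the literal reading. The abnormal count for these changes is then (1 − *s*) times what it should be. If *s* is the same in every arm, the difference between active cream and Vehicle shrinks by the same factor. The documents give neither *s* nor the rate of such changes, so *s* can only be bounded: 0 (no error) to 1 (all missed).

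**5. Other scheduled capture**

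The diary in Appendix 14 has seven concern items: redness, stinging, burning, heaviness, stickiness, spreading and oiliness. None names thinning or pigment change. The slit-lamp skin grade is the only scheduled item that names those two signs.

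**6. Related clarification**

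SAP 4.8.6 names 8 of the 12 graded items. The 12 − 8 = 4 unnamed (4/12 = 33%) are anterior chamber cells, flare, lens pathology and sclera. The SAP wording is inclusive and all data are listed, so this is a gap in clarity and not a contradiction.

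**The case against.** The strongest reply is that no ophthalmic investigator will grade dermatitis as normal. The surrounding lines make the intent plain, and no document shows that anyone miscoded. That is fair: the true effect may be zero. It does not justify leaving a safety grade that works only if raters reverse its written definition.

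The second reply is that adverse events cover the gap. A new skin change seen at the exam can meet the definition, "Any untoward medical occurrence associated with the use of an IP in humans, whether or not considered drug related", whatever its grade. It would then reach the by-arm ocular adverse event tables, whose treatment-emergent overview is a topline table, whereas Table 14.4.2.5 is descriptive and not topline. For dermatitis, the daily diary items on redness, stinging and burning also help. This stands as a real but partial backstop. Section 8.3 says "simple questions with minimal suggestions or implications should be used as the initial questions", and thinning or pigment change is not something subjects are prompted to mention.

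Third, investigators are masked and Appendix 5 asks for the same manner of examination throughout a site, so a literal reading should not favour an arm in the coding. That is also right. The consequence is an undercount and a diluted contrast, not a bias in how the arms are coded.

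Finally, this is a drafting error and not a deliberate design choice, and the SAP 4.8.6 point is separate and minor. Both are accepted.

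**Conclusion.** The concern holds and should be fixed. As written, the key codes thinning, pigment change and dermatitis of the treated skin as Normal, and nothing else in the protocol or SAP corrects it. Confidence is high on the text and cannot be high on the effect. What is at risk is the by-arm eyelid skin count in Table 14.4.2.5, not skin safety capture as a whole.

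This rests on two assumptions: that the 0/1 grade is entered for every eye, as the SAP summary implies but Appendix 5 does not spell out, and that no eCRF completion guide outside the two documents already corrects the line.

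**What to change.** - **Reword the key** in Appendix 5, and in any eCRF guide that repeats it. Grade 0: *Normal, no skin changes*. Grade 1: *Abnormal, for example thinning, pigment change or dermatitis*. This settles both explanations of the slip.
- **Implement it** with IRB approval first, as Protocol section 12.1 requires, and a memo to the 10–16 sites.
- **Look back while masked.** Ask each site how it applied the line and query the skin entries already made. This may recover little, because changes regarded as Normal need no source note; report that as a limitation.
- **Flag grades by key version** if the correction takes effect after grading has begun. The cohorts enrol in sequence and SAP 4.2.3 pools Vehicle across them, so a change of key between cohorts could look like a dose difference.
- **Clarify the SAP** by naming anterior chamber cells, flare, lens pathology and sclera in section 4.8.6 and Table 14.4.2.5.

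The cost is a correction to one item of the appendix with its approval, one memo, one masked question and query round, a version flag if needed, and four named rows of data already collected.

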APPENDIX 6: IOP MEASUREMENT

IOP measurements will be performed utilizing Goldmann applanation tonometry according to the Investigator's standard procedure. All pressures will be recorded in mmHg.

APPENDIX 7: DILATED OPHTHALMOSCOPY

Dilated Ophthalmoscopy will include assessment of the retina for any abnormal findings, optic nerve head for pallor and cupping (cup to disc ratio). After the Ophthalmoscopy procedure, the Investigator will determine if findings are within normal limits or are abnormal. For abnormal findings at Visit 1, the Investigator will determine whether or not the abnormality would exclude subject from study participation.

APPENDIX 8: EYE DISCOMFORT, EYE DRYNESS SYMPTOM ASSESSMENT

Symptom Assessment Visual Analog Scale (VAS)

Subjects will be asked the following questions regarding their current symptoms (unrelated to Investigational Product instillation) at each visit.

The subject will be asked to subjectively rate each ocular symptom (OU) by placing a vertical mark on the horizontal line to indicate the level of eye discomfort and dryness. 0 corresponds to “No Symptoms” and 100 corresponds to “Severe Symptoms”

Subject Instructions: Please review the symptoms below. After your review, please rate how your eyes feel for each of the following symptoms by placing a single vertical mark that represents how your symptom feels at this moment.

0 = No Symptoms and 100 = Severe Symptoms

Eye Discomfort	0	100

Eye Dryness	0	100

APPENDIX 9: MODIFIED BLISS

Check each box which most reflects the frequency of each symptom.

Symptoms	None of the time	Occasionally	Frequently	All of the time
Eyes that itch				
Eyes that burn				
Eyelids feel heavy or puffy				
Feel like something in your eye				
Dry eyes				
Gritty eyes				
Irritated eyes				
Eyes that tear or water				
Crusty eyes				
Eyelids that are stuck together				
Red eyes or eyelids				

<https://www.nei.nih.gov/learn-about-eye-health/eye-conditions-and-diseases/blepharitis>

APPENDIX 10: TEAR BREAK-UP TIME (TBUT)

TBUT will be measured at each visit. To measure TBUT, fluorescein is instilled into the subject's tear film, the subject is allowed to blink once or twice to disperse the fluorescein, after approximately 30 seconds the subject is then asked not to blink while the tear film is observed under a broad beam of cobalt blue illumination using a slit-lamp.

[figure not shown]
[figure not shown]
Using a stopwatch the TBUT is recorded as the number of seconds that elapse between the last blink and the appearance of the first dry spot in the tear film. The time is measured to hundredth and using normal rounding rules, rounded to tenths. A TBUT under 10 seconds is considered abnormal.

A total of 2 measurements are obtained and entered into the record. If the 2 measurements are > 2 seconds apart then a third measurement is obtained and the closest 2 measurements are recorded.

NOTE: The TBUT and the FCS may be performed right eye then left eye or staggered with the TBUT for the left eye being done during the waiting period before completing the FCS for the right eye.

**APPENDIX 11: FLUORESCEIN CORNEAL STAINING (FCS) / NATIONAL EYE INSTITUTE /
INDUSTRY WORKSHOP SCALE**

The 5 areas of the cornea will be scored by the investigator according to the following scoring system and the total score will also be calculated. NOTE: The TBUT and the FCS may be performed right eye then left eye or staggered with the TBUT for the left eye being done during the waiting period before completing the FCS for the right eye.

APPENDIX 12: UNANESTHETIZED SCHIRMER TEST

The Schirmer test will be conducted on unanesthetized eyes. A 35 mm x 5 mm filter paper strip is used to measure the amount of tears that are produced over 5 minutes. The strip is placed in the lower eyelid margin without the use of a preplaced ophthalmic anesthetic drop. After 5 minutes, the strip is removed and the amount of wetting is measured in millimeters. The wetting margin on the Schirmer strip is marked with a pen and the strip is placed in the subject's source document.

